7.1 Trial Treatments

The treatment to be used in this trial is outlined below in Table 4

Table 4 Trial Treatment

Drug	Dose/Potency	Dose Frequency	Route of Administration	Regimen/Treatment Period	Use
Therapeutic Agent					
Pembrolizumab	200 mg	Every 3 weeks (+15 days)	IV infusion	Day 1 of each 3 week cycle	Experimental
Imaging Agent					
Ferumoxylol		Baseline, 12 weeks post radiation, anytime there is suspected radiographic progression and 6 weeks after suspected radiographic progression (± 15 days).	IV infusion	Baseline, 12 weeks post radiation, anytime there is suspected radiographic progression and 6 weeks after suspected radiographic progression (± 15 days).	

Trial treatment should begin on the day of randomization or as close as possible to the date on which treatment is allocated/assigned.

7.1.1 Timing of Dose Administration

Pembrolizumab: Trial drug treatment should be administered on Day 1(+15 days) of each cycle after all procedures/assessments have been completed as detailed on the Trial Flow Chart (Section 6.0). Pembrolizumab will not be administered less than 14 days after any major surgeries including brain biopsy.

All trial treatments will be administered on an outpatient basis.

Pembrolizumab 200mg will be administered as IV infusion every 3 weeks as per institutional guidelines. The expiration of the reconstituted pembrolizumab is 6 hours at room temperature and 20 hours refrigerated. The total cumulative storage time at room temperature and refrigeration should not exceed 24 hours. The Pharmacy Manual contains specific instructions for the preparation of the Pembrolizumab infusion fluid and administration of infusion solution.

Ferumoxytol (only for study MRIs): The total dose of ferumoxytol will be 7mg/kg (not exceeding 510mg total). The ferumoxytol will be mixed with normal saline 1:1 solution to dilute to 15mg/ml. 1 mg/Kg IV will be injected at the start of the 7th dynamic cycle during the DSC acquisition at a flow rate of 3ml/s followed by 20ml saline flush. The rest of the ferumoxytol will be given as IV injections at a low flow rate (.1ml/s) followed by 20 mL saline flush. The flow rates may be adjusted at the physician's discretion.

Vitals monitoring for ferumoxytol MRIs: Blood pressure and pulse will be taken at the start of MRI (\pm 5 minutes), after each ferumoxytol injection (\pm 5 minutes), and again 30 minutes (\pm 5 minutes) after the first injection of ferumoxytol.

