Fatal and serious hypersensitivity reactions including anaphylaxis have occurred in patients receiving Feraheme. Initial symptoms may include hypotension, syncope, unresponsiveness, cardiac/cardiorespiratory arrest.

- Only administer Feraheme when personnel and therapies are immediately available for the treatment of anaphylaxis and other hypersensitivity reactions.
- Observe for signs or symptoms of hypersensitivity reactions during and for at least 30 minutes following Feraheme infusion including monitoring of blood pressure and pulse during and after Feraheme administration.
- Hypersensitivity reactions have occurred in patients in whom a previous Feraheme dose was tolerated.

In the black box warning the FDA updated their recommendations of how ferumoxytol should be given. The option to give ferumoxytol (510mg) as a fast undiluted injection in approximately 1 minute has been removed. It was recommended that ferumoxytol (510mg) be given over at least 15 minutes. To accommodate for this, the dose of ferumoxytol in this study will be given in a minimum of two separate, fractionated doses. The rate of administration of the second dose will be slowed down to no faster than .1 mL/s.

Post-Marketing Safety

AMAG's pharmacovigilance system proactively reviews spontaneous reports. Routine surveillance of events is performed daily and monthly signal detection and evaluation processes monitor and update the safety profile. To date the information received from the post-marketing setting is consistent with the known safety profile of ferumoxytol.

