Based on communication with AMAG Pharmaceuticals, manufacturer of ferumoxytol, all recommendations apply to iron replacement therapy where infusion rate and dilution do not impact efficacy. However, for an imaging indication certain infusion parameters are required to gain information, such as dynamic imaging. Increased infusion rate will only affect the first injection of 1 mg/kg, which is a small fraction of the full therapeutic dose, and therefore may minimally increase the risk of adverse reactions. The next two injections are given at a slower rate. The recommended 15 minutes has no scientific basis, it has been chosen arbitrarily. For MR imaging stopping the scanner for 15 minutes would be disadvantageous. Applying multiple injections, which is not the case with iron replacement therapy, may increase safety, compared to continuous injection. This may contribute to the fact that in our patient population only minor adverse reactions have been reported.

OHSU Toxicity Data

As of December 31st, 2015, a total of 671 infusions of ferumoxytol had been completed on 331 study subjects as part of OHSU’s Blood Brain Barrier sponsored IRB approved protocols. The dose has ranged from 75 to 510 mg of ferumoxytol (0.5 to 11 mg/kg). In all these cases, ferumoxytol was given during MRI, using multiple IV bolus injections (1:1 diluted ferumoxytol, 3ml/s flow rate, with 20ml saline flush at the same flow rate.) In most studies the first 1mg/kg (or 75mg) was used for dynamic perfusion imaging; the remaining dose was injected in one or two subsequent bolus injections. The full 510mg was never given as a single injection. Within 42 days after ferumoxytol administration, there were 85 adverse events possibly, probably or definitely related to ferumoxytol. Among the 85 events, 43 patients had 1 event, 12 had 2 events, 3 had three events, one had 4 events and one had five events. 80% of the toxicity events occurred within 48 hours post ferumoxytol administration. There were no severe, grade 4 or 5 toxicities (CTCAE version 3 and 4) that were attributed to ferumoxytol. Table 2 shows the toxicities up to and beyond 48 hours. (Data has been submitted for publication in December of 2016)

Toxicity Category Attribute	Overall (<42 days)		Within 48 hours		>48 hours	
	# of events	Freq of events	# of events	Freq of events	# of events	Freq of events
Gastrointestinal	31	4.62%	23	3.43%	8	1.19%
Cardiac General	17	2.53%	17	2.53%	0	0.00%
Pain	17	2.53%	17	2.53%	0	0.00%

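### The last timed vital-sign check after ferumoxytol runs from the first injection, while the boxed warning the protocol quotes counts its 30 minutes from the infusion

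*Combined protocol and SAP*

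**What the plan says.** Section 7.1.1, repeated in 7.4.3, lists the vital signs for each ferumoxytol MRI: blood pressure and pulse at the start of the scan, after every injection, and a last time 30 (±5) minutes "after the first injection of ferumoxytol".

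Section 4.8 quotes the boxed warning on fatal and serious hypersensitivity. It asks for observation "during and for at least 30 minutes following Feraheme infusion including monitoring of blood pressure and pulse during and after Feraheme administration". As the study's accommodation to the revised labelling, Section 4.8 says that "the dose of ferumoxytol in this study will be given in a minimum of two separate, fractionated doses" and that "The rate of administration of the second dose will be slowed down to no faster than .1 mL/s". Further on, the same section describes a first injection of 1 mg/kg and adds that "The next two injections are given at a slower rate".

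Section 7.1.1 sets the total at 7 mg/kg with a ceiling of 510 mg. The first 1 mg/kg goes in at 3 mL/s and the rest at 0.1 mL/s. It then adds: "The flow rates may be adjusted at the physician's discretion". Section 8.3 repeats the dosing text, including this sentence.

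**The concern.** The two texts use different clocks. The warning counts from the infusion; the operative schedule counts from an injection that carries one seventh of the dose, or up to about one fifth in a 100 kg subject once the ceiling applies. Staff work from Sections 7.1.1 and 7.4.3, not from the background section. They could follow both to the letter and still have no check scheduled 30 minutes after the infusion ended.

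The exposure is repeated. Table 4 schedules ferumoxytol at baseline, at 12 weeks, at any suspected progression and 6 weeks after that. The quoted warning notes reactions in patients who had tolerated an earlier dose.

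A secondary question is whether the discretion over flow rates is subject to the limit in Section 4.8, since Sections 7.1.1 and 8.3 attach no upper bound to it.

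**Working it through.** **The plan's own figure.** Section 11.1 gives 510 mg in 17 mL, so 510/17 = 30 mg/mL. Diluted 1:1 this is 15 mg/mL, as Section 7.1.1 states.

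**Inputs from Section 7.1.1.** Total dose = the smaller of 7 mg/kg and 510 mg (ceiling reached at 510/7 = 72.9 kg). First injection 1 mg/kg at 3 mL/s, then a 20 mL flush. Remainder at 0.1 mL/s. Last check at 30 ± 5 minutes from the first injection.

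**Assumptions.** Body weights of 50, 72.9 and 100 kg as illustrations. First flush at 3 mL/s (20/3 = 6.7 s). No pause between injections, which is the case most favourable to the plan. Dosing ends when the last ferumoxytol is in; the final flush is not counted.

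**Formulas.**
- Share given after the clock starts = (total − first)/total.
- Slow-injection time = (remainder/15)/0.1 seconds.
- End of dosing = first injection + first flush + slow injection.
- Interval from end of dosing to last check = 25, 30 or 35 minutes − end of dosing.

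| Weight (kg) | Total (mg) | Remainder (mg) | Share after clock starts | Slow injection | End of dosing | Last check after end of dosing: −5 / nominal / +5 (min) |
|---|---|---|---|---|---|---|
| 50 | 350 | 300 | 85.7% | 20.0 mL, 200 s = 3.33 min | 1.1 + 6.7 + 200 s = 3.46 min | 21.5 / 26.5 / 31.5 |
| 72.9 | 510 | 437 | 85.7% | 29.1 mL, 291 s = 4.86 min | 1.6 + 6.7 + 291 s = 5.00 min | 20.0 / 25.0 / 30.0 |
| 100 | 510 | 410 | 80.4% | 27.3 mL, 273 s = 4.56 min | 2.2 + 6.7 + 273 s = 4.70 min | 20.3 / 25.3 / 30.3 |

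With no pause, the nominal check therefore falls 3.5 to 5.0 minutes short of 30 minutes after dosing. The +5 limit reaches 30 minutes, with 1.5 minutes to spare at 50 kg and essentially none at 72.9 kg.

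**Effect of a pause.** The documents give no interval between injections. Each minute of pause takes one minute off every figure in the last column. An assumed 5-minute pause gives 20.0 to 21.5 minutes nominally. An assumed 10-minute pause gives 15.0 to 16.5 nominally, 10.0 to 11.5 at −5 and 20.0 to 21.5 at +5.

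**Search for a rule that closes the gap.** Section 9.5.3 asks for monitoring after administration but refers back to the study protocol for how. Section 4.8 argues against the recommended 15-minute infusion time; it says nothing against the 30-minute observation. No section of the available text sets a period after the last injection.

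**The case against.** Several points on the other side are sound.

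- **There is a reading after the last injection.** Vital signs follow every injection, so the largest part of the dose is not left unchecked, and the warning's request for readings during and after administration is met. That reading does not cover the following 30 minutes.
- **A reading is not an observation period.** A reader might infer that subjects are observed for less than 30 minutes after most of the dose. The documents do not support that. The warning asks for observation and names no reading at minute 30, and neither 7.1.1 nor 7.4.3 says that observation stops at the last reading. What stands is narrower: no post-dose period is stated, and the only timed check runs from a different event.
- **The documented shortfall is small.** With no pause it lies within the ±5-minute window. A reader might take 10 or 15 minutes after dosing as the plan's figure; those values rest wholly on an assumed pause.
- **Other safeguards exist.** Section 4.8 reports 671 administrations at the institution, by multiple bolus injections, with no severe, grade 4 or grade 5 toxicity attributed to ferumoxytol. Section 9.5.3 requires personnel and therapies to be at hand and the infusion to be stopped on a reaction. Section 5.2 excludes subjects with relevant hypersensitivity. Section 4.8 also argues that the labelling recommendations concern iron replacement and that split injections may be safer. None of this says from which event the 30 minutes run.
- **The rate wording is not a proven contradiction.** A reader might infer that 7.1.1 allows the limit in 4.8 to be exceeded. Sections 7.1.1 and 8.3 give the same 0.1 mL/s, and an adjustment may mean slowing down. It is an ambiguity, because no upper bound is attached to the discretion.

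**Conclusion.** The inconsistency is real and modest in documented size. Sections 7.1.1 and 7.4.3 start the 30-minute clock at the first injection, before 80 to 86% of the dose is given. The warning in Section 4.8 starts it at the infusion, and no available section bridges the two or justifies a departure.

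On the documents alone, with injections back to back, the last scheduled check comes about 25 to 27 minutes after dosing ends, with a range over the tolerance window of about 20 to 32 minutes. This rests on the stated 0.1 mL/s, the assumed first-flush rate and weights of 50 to 100 kg. Any pause for scanning lowers it; the amount cannot be known from the text.

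This is a matter of safety monitoring. Sample size, the reference standard and the primary analysis of sensitivity and specificity are untouched.

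**What to change.** Reconcile Sections 7.1.1 and 7.4.3 with the warning quoted in Section 4.8 on the event from which the 30 minutes run. If the sponsor intends a departure from the quoted warning, the protocol should state it and give the reason. Which rule applies is for the sponsor and the investigators to decide.

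Secondly, make clear in Sections 7.1.1 and 8.3 whether the discretion over flow rates is subject to the limit in Section 4.8.

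The cost is wording in three sections and, depending on what is decided, possibly a few minutes of monitoring per scan.

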7.2 Study procedures narrative

Enrolled subjects will receive pembrolizumab (200 mg I.V. every 3 weeks) starting on the first day of radiation (\pm 15 days) until persistent radiographic progression is confirmed. [Subjects may receive standard of care cytotoxic chemotherapy \(carboplatin and pemetrexed\) while on trial, at the treating physician's discretion.](#) [72, 73] MRI scans will be performed to assess response to therapy. Clinical standard of care MRIs are done at baseline, 12 weeks post radiation and then every 9 weeks thereafter until suspected radiographic progression. An early follow up clinical standard of care MRI will be performed 6 weeks (\pm 15 days) from the date of MRI showing suspected radiographic progression to confirm persistent radiographic progression. Clinical scans may be done more frequently, based on physician's discretion. Each MRI scan will be evaluated for progression.

Additional ferumoxytol steady state MRIs will be done at baseline, 12 weeks after radiation, at suspected radiographic progression and within 6 weeks (\pm 15 days) from suspected radiographic progression to confirm persistent radiographic progression.

When persistent radiographic progression is confirmed, subjects will be evaluated for a craniotomy with intent to complete resection and /or biopsy of the enhancing lesion, if this is thought to be the clinical standard of care.

Biopsy tissue obtained from surgery at persistent radiographic progression will be evaluated by the pathologists at OHSU. The pathologist will determine if the tissue is consistent with progression or pseudoprogression, where progression is defined as presence of viable metastatic carcinoma in the biopsy tissue and absence of tumor cell is assumed to reflect pseudoprogression. If histopathology confirms pseudoprogression the subject will continue on pembrolizumab every 3 weeks until further radiographic progression is suspected. If histopathology confirms progression, the subject will be removed from the study, followed clinically with serial clinical stand of care MRIs every 3 months for up to a year and then every 6 months until death or lost to follow-up.

The decision regarding surgery will be consensus based and will be made after each individual case has been presented at the OHSU interdisciplinary brain tumor board. If a subject is not a surgical candidate, or is unwilling to undergo surgery, they will be taken off study. They will, however, be eligible for continuation of pembrolizumab, at the physician's discretion, at the same dose and frequency, if clinical benefit is noted. They will be followed clinically with serial clinical standard of care MRI scans every 3 months for up to a year and then every 6 months until death or until lost to follow up. These subjects will not be included in the analysis the primary end-points but will be included in the survival analysis.

In subjects where the lesion remains unchanged or regresses in volume at 6 weeks) after the date of suspected radiographic progression, pembrolizumab will be continued until further persistent radiographic progression is confirmed.

All subjects will be followed with clinical examination and clinical standard of care MRI scans until death or lost to follow up. Subjects will be treated for up to 2 years, toxicity, or progression whichever comes first. Dose reductions/discontinuations for pembrolizumab will be as per Merck guidelines.

Pembrolizumab may be stopped for up to 3 months in the context of a craniotomy to confirm persistent radiographic progression or unrelated major surgery. Dosing delays of up to 7 days are permitted at physician discretion for medical / surgical events or logistical reasons. Dosing interruptions (missing a dose) are permitted in the case of medical / surgical events or logistical reasons not related to study therapy (e.g., elective surgery, medical events, subject vacation, and/or holidays), not to exceed two consecutive doses or a maximum of 9 weeks. The reason for interruption will be documented in the subject's study record. Pembrolizumab will not be administered less than 14 days after any major surgeries including brain biopsy.

7.3 Informed Consent

The Investigator must obtain documented consent from each potential subject prior to participating in a clinical trial.

Consent must be documented by the subject's dated signature or by the subject's legally acceptable representative's dated signature on a consent form along with the dated signature of the person conducting the consent discussion.

A copy of the signed and dated consent form should be given to the subject before participation in the trial.

The initial informed consent form, any subsequent revised written informed consent form and any written information provided to the subject must receive the IRB/ERC's approval/favorable opinion in advance of use. The subject or his/her legally acceptable representative should be informed in a timely manner if new information becomes available that may be relevant to the subject's willingness to continue participation in the trial. The communication of this information will be provided and documented via a revised consent form or addendum to the original consent form that captures the subject's dated signature or by the subject's legally acceptable representative's dated signature.

Specifics about a trial and the trial population will be added to the consent form template at the protocol level.

The informed consent will adhere to IRB/ERC requirements, applicable laws and regulations and Sponsor requirements.

7.4 Trial Procedures

See the Schedule of Events for when tests should be completed.

7.4.1 Clinical procedures:

- Demographics
- Medical history
- Prior medication review
 - The investigator or qualified designee will review prior medication and herbal and dietary supplement use, including any protocol-specified washout requirement, and record prior medication taken by the subject within 28 days before starting the trial. Treatment for the disease for which the subject has enrolled in this study will be recorded separately and not listed as a prior medication.
 - The investigator or qualified designee will record medication, if any, taken by the subject during the trial. All medications related to reportable SAEs and ECIs should be recorded as defined in Section 7.2.
 - Subjects will be asked to stop all nonprescription herbal supplements and over the counter medication.
- Full physical examination
- Vital signs
 - temperature, pulse, respiratory rate, height, weight and blood pressure. Height will be measured at screening only.
- ECOG performance status (Appendix)
- Archival tissue collection:
 - If available, any tumor biopsy tissue (lung, mediastinal, or brain) that was obtained prior to screening for the study will be requested and sent to the Merck-designated Contract Research Organization (CRO) QualTek Molecular Laboratories for PD-1 biomarker assay.
- Biopsy or resection of metastatic brain lesion
 - When clinically indicated, a biopsy or resection will be done of the brain lesion(s) 1) prior to enrollment and SRS, and 2) at the time of persistent radiographic progression. Any tumor biopsy tissue will be sent to the Merck-designated Contract Research Organization (CRO) QualTek Molecular Laboratories for PD-1 biomarker assay.
- Radiation therapy:
 - All patients will receive standard of care stereotactic radiosurgery in 1-5 fractions, at the discretion of the treating radiation oncologist. If all lesions cannot be treated on the same day, all lesions MUST be treated ≤ 14 days of treatment of the first lesion. Gamma knife or X-rays with nominal energy of 4 megavoltage (MV) or greater for accelerator-based treatments, including

isocentric conical collimators, mini-multi-leaf (5 mm or less) technology or linear accelerators mounted on robotic arms will be used to deliver the target dose.

- Target Volume: The volumes shall be defined by a planning MRI brain scan, with the patient in the treatment position. The target volume should include the enhancement seen on planning MRI with 0-1 mm margin. The maximal cross-sectional diameter must be < 3.0 cm for a lesion treated with a single fraction.
- Target Dose: The dose should be prescribed to the highest isodose line encompassing the 90-95% target volume. General dose guidelines are as follows
 - Lesion diameter < 1cm – 20-22 Gy in 1 fraction
 - Lesion diameter 1-2 cm – 18-20 Gy in 1 fraction
 - Lesion diameter 2-3 cm – 18 Gy in 1 fraction, or 27 Gy in 3 fraction or 30-35 Gy in 5 fractions
 - Lesion diameter 3-5cm – 30 – 35 Gy in 5 fractions
- Up to 8 of dexamethasone can be administered on the day of single fraction SRS, at the discretion of the treating physician.
- Radiation therapy to an additional symptomatic solitary lesion or to the brain may be allowed at the investigator's discretion at any time during the study if :
 - they fulfill other criteria to remain in the study and
 - this lesion has remained stable or shows radiographic response compared to baseline.
 - this additional lesion was not in the initial radiation field.
- Subjects may receive standard of care cytotoxic chemotherapy (carboplatin and pemetrexed) while on trial, at the treating physician's discretion. Chemotherapy to be administered per package insert.
- Subject may also provide consent/assent for future correlative research (optional). Subjects may participate in the main trial without participating in future correlative research.

7.4.2 Lab tests: see Table 5

- CBC with differential
- Comprehensive serum chemistry panel
- Urinalysis
- FT4, TSH
- PT/INR
- aPTT
- Pregnancy test (urine or serum) (women). If the urine test is positive, cannot be performed or cannot be confirmed as negative, a serum pregnancy test will be required.
- Serum biomarker assay (see Section 8.5.1)

Table 5 Laboratory Tests

Hematology	Chemistry	Urinalysis	Other
Hematocrit	Albumin	Blood	Serum β -human chorionic gonadotropin [†]
Hemoglobin	Alkaline phosphatase	Glucose	(β -hCG) [†]
Platelet count	Alanine aminotransferase (ALT)	Protein	PT (INR)
WBC (total and differential)	Aspartate aminotransferase (AST)	Specific gravity	aPTT
Red Blood Cell Count	Carbon Dioxide ‡	Microscopic exam (If abnormal)	Free thyroxine (T4)
Absolute Neutrophil Count	(CO₂ or bicarbonate)	results are noted	Thyroid stimulating hormone (TSH)
Absolute Lymphocyte Count	Calcium	Urine pregnancy test [†]	
	Chloride		Blood for correlative studies
	Glucose		
	Potassium		
	Sodium		
	Total Bilirubin		
	Direct Bilirubin (If total bilirubin is elevated above the upper limit of normal)		
	Total protein		

Laboratory tests for screening or entry into the Second Course Phase should be performed within 10 days prior to the first dose of treatment. After Cycle 1, pre-dose laboratory procedures can be conducted up to 72 hours prior to dosing. Results must be reviewed by the investigator or qualified designee and found to be acceptable prior to each dose of trial treatment.

